### 13.2.3 Exploratory/Correlative Analyses

The exploratory objectives are to investigate paired, serial biopsy specimens from pre-treatment and 8-12 weeks after starting treatment for the following:

- MHC class I expression (scored by pathologist)
- Number of infiltrating T cells per mm^2
- Tumor associated macrophage number and phenotype using multiplex immunohistochemistry
- T cell clonality
- Gene expression profiling

Additionally, the exploratory objectives include investigating peripheral blood samples from patients to determine:

- The number and phenotype of T cells specific for CT antigens and potential neo-antigens
- The phenotype and activation state of circulating monocytes and PBMC
- Cytokines associated with response

The exploratory outcomes will be summarized with descriptive statistics for all the biomarkers described above.

#### 13.2.4 Sample Size and Power

A Simon 2-stage design will be used: Twelve patients will be enrolled initially. If 0 respond the study will be stopped for futility. The probabilities of stopping the trial for futility at this interim analysis are 54% and 3% under the null hypothesis (ORR=5%) and alternative hypothesis (ORR=25%) respectively.

Otherwise, an additional four patients will be enrolled. If three or more out of 16 patients respond, the treatment will be considered promising and would likely lead to widespread use of this regimen in the clinic. The overall type I error for the study is 4.3%, and the overall power of the study at the alternative hypothesis (ORR=25%) is 80.1%.

The patient demographics for the addendum is expected to be similar to the patient demographics of the original protocol. The planned enrollment report is given below.

#### 13.2.5 Planned Enrollment Report

Racial Categories	Ethnic Categories				Total	
	Not Hispanic or Latino		Hispanic or Latino			
	Female	Male	Female	Male		
American Indian/Alaska Native						
Asian	1	1			2	
Native Hawaiian or other Pacific Islander						

NCI Protocol #: CITN-13  
Version Date: March 03, 2020

Black or African American	1	1			2
White	5	5	1	1	12
More than one race					
Total					16

**APPENDIX A            PERFORMANCE STATUS CRITERIA (TREATMENT GROUP 1 AND 2)**

ECOG Performance Status Scale		Karnofsky Performance Scale	
Grade	Descriptions	Percent	Description
0	Normal activity. Fully active, able to carry on all pre-disease performance without restriction.	100	Normal, no complaints, no evidence of disease.
		90	Able to carry on normal activity; minor signs or symptoms of disease.
1	Symptoms, but ambulatory. Restricted in physically strenuous activity, but ambulatory and able to carry out work of a light or sedentary nature (e.g., light housework, office work).	80	Normal activity with effort; some signs or symptoms of disease.
		70	Cares for self, unable to carry on normal activity or to do active work.
2	In bed <50% of the time. Ambulatory and capable of all self-care, but unable to carry out any work activities. Up and about more than 50% of waking hours.	60	Requires occasional assistance, but is able to care for most of his/her needs.
		50	Requires considerable assistance and frequent medical care.
3	In bed >50% of the time. Capable of only limited self-care, confined to bed or chair more than 50% of waking hours.	40	Disabled, requires special care and assistance.
		30	Severely disabled, hospitalization indicated. Death not imminent.
4	100% bedridden. Completely disabled. Cannot carry on any self-care. Totally confined to bed or chair.	20	Very sick, hospitalization indicated. Death not imminent.
		10	Moribund, fatal processes progressing rapidly.
5	Dead.	0	Dead.

## **APPENDIX B CTEP MULTICENTER GUIDELINES (TREATMENT GROUP 1 AND 2)**

If an institution wishes to collaborate with other participating institutions in performing a CTEP-sponsored research protocol, then the guidelines below must be followed.

### Responsibility of the Protocol Chair

- The Protocol Chair will be the single liaison with the CTEP Protocol and Information Office (PIO). The Protocol Chair is responsible for the coordination, development, submission, and approval of the protocol as well as its subsequent amendments. The protocol must not be rewritten or modified by anyone other than the Protocol Chair. There will be only one version of the protocol, and each participating institution will use that document. The Protocol Chair is responsible for assuring that all participating institutions are using the correct version of the protocol.
- The Protocol Chair is responsible for the overall conduct of the study at all participating institutions and for monitoring its progress. All reporting requirements to CTEP are the responsibility of the Protocol Chair.
- The Protocol Chair is responsible for the timely review of Adverse Events (AE) to assure safety of the patients.
- The Protocol Chair will be responsible for the review of and timely submission of data for study analysis.

### Responsibilities of the Coordinating Center

- Each participating institution will have an appropriate assurance on file with the Office for Human Research Protection (OHRP), NIH. The Coordinating Center is responsible for assuring that each participating institution has an OHRP assurance and must maintain copies of IRB approvals from each participating site.
- Before the activation of the protocol at each participating institution, an OHRP form 310 (documentation of IRB approval) must be submitted to the CTEP PIO.
- The Coordinating Center is responsible for central patient registration. The Coordinating Center is responsible for assuring that IRB approval has been obtained at each participating site before the first patient registration from that site.
- The Coordinating Center is responsible for the preparation of all submitted data for review by the Protocol Chair.
- The Coordinating Center will maintain documentation of AE reports. There are two options for AE reporting: (1) participating institutions may report directly to CTEP with a copy to the Coordinating Center, or (2) participating institutions report to the Coordinating Center who in turn report to CTEP. The Coordinating Center will submit AE reports to the Protocol Chair for timely review.
- Audits may be accomplished in one of two ways: (1) source documents and research records for selected patients are brought from participating sites to the Coordinating Center for audit, or (2) selected patient records may be audited on-site at participating sites. If the NCI chooses to have an audit at the Coordinating Center, then the Coordinating Center is responsible for having all source documents, research records, all IRB approval documents,

NCI Drug Accountability Record forms, patient registration lists, response assessments scans, x-rays, etc. available for the audit.

Inclusion of Multicenter Guidelines in the Protocol

- The protocol must include the following minimum information:
  - The title page must include the name and address of each participating institution and the name, telephone number and e-mail address of the responsible investigator at each participating institution.
  - The Coordinating Center must be designated on the title page.
  - Central registration of patients is required. The procedures for registration must be stated in the protocol.
  - Data collection forms should be of a common format. Sample forms should be submitted with the protocol. The frequency and timing of data submission forms to the Coordinating Center should be stated.
  - Describe how AEs will be reported from the participating institutions, either directly to CTEP or through the Coordinating Center.
  - Describe how Safety Reports and Action Letters from CTEP will be distributed to participating institutions.

Agent Ordering

- Except in very unusual circumstances, each participating institution will order DCTD-supplied investigational agents directly from CTEP. Investigational agents may be ordered by a participating site only after the initial IRB approval for the site has been forwarded by the Coordinating Center to the CTEP PIO.

## APPENDIX C BIOASSAY TEMPLATES

### Mycosis Fungoides/Sézary Syndrome (Treatment Group 1)

Biomarker Name a AND Lead PI and Site	Assay (CLIA: Y/N)	Use (Integral, Integrated, or Exploratory) AND Purpose b	Tissue/Body Fluid Tested and Timing of Assay	M/O	Funding Source(s) c
Tissue PDL1 Expression  PI: [name]  Site: Fred Hutchinson Cancer Research Center	Chromagenic (Single-Color) IHC for PD-L1  CLIA: N	Exploratory  Purpose: We will explore correlation of PDL1 expression with response. Two hypotheses will be explored:  1) Pre-treatment PDL1 expression correlates with response  2) Interferon-gamma mediated upregulation of PDL1 correlates with response	Tissue: Skin biopsy  Timing:  (M) Prior to IFN-gamma lead-in, Prior to Cycle 1, Prior to Cycle 2, w at progression or appearance of a new lesion, at end of treatment, and in the event of a Skin Flare Reaction  (O) At response (PR/CR),	M	Funding for biomarkers will be from CITN with co-funding from Merck and Horizon. Additional funds will be sought from foundations and CTEP's CRADA with Merck
Spatial association of tumor cells and components of the tumor microenvironment  PI: [name]  Site: Fred Hutchinson Cancer Research Center	Multispectral immunohistochemistry  CLIA: N	Exploratory  Purpose: Hypothesis generating  Multispectral immunohistochemistry IHC for PD1, PDL1, PDL2, CD3, CD4, CD8, Foxp3, CD163 will define the spatial relationship of the tumor infiltrate	Tissue: Skin biopsy  Timing:  (M) Prior to IFN-gamma lead-in, Prior to Cycle 1, Prior to Cycle 2, at progression or appearance of a new lesion, r, at end of treatment, and in the event of a Skin Flare Reaction  (O) At response (PR/CR),	M	(see above)
High dimensional imaging of tumor microenvironment  PI: [name]  Site: Stanford University	Multiplexed Ion Beam Imaging  CLIA: N	Exploratory  Purpose: Hypothesis generating  Mass spectroscopy based imaging of ~30 parameters simultaneously to delineate expression of immune checkpoint molecules and activation markers on components of the tumor microenvironment	Tissue: Skin biopsy  Timing:  (M) Prior to IFN-gamma lead-in, Prior to Cycle 1, Prior to Cycle 2, , at progression or appearance of a new lesion, at end of treatment and in the event of a Skin Flare Reaction  (O) At response (PR/CR).	M	(see above)

NCI Protocol #: CITN-13  
 Version Date: March 03, 2020

Biomarker Name a AND Lead PI and Site	Assay (CLIA: Y/N)	Use (Integral, Integrated, or Exploratory) AND Purpose b	Tissue/Body Fluid Tested and Timing of Assay	M/O	Funding Source(s) c
Gene expression profiling  PI: [name]  Site: Fred Hutchinson Cancer Research Center	Nanostring immune panel  CLIA: N	Exploratory  Purpose: Hypothesis generating and will assess Th1 skewing of T cells after interferon gamma treatment	Tissue: Skin biopsy and peripheral blood mononuclear cells  Timing:  (M) Skin biopsy: Prior to IFN-gamma lead-in, Prior to Cycle 1, Prior to Cycle 2, at progression or appearance of a new lesion, at end of treatment and in the event of a Skin Flare Reaction  Blood draw: Prior to IFN-gamma lead-in, Prior to Cycle 1, Prior to Cycle 2, Prior to Cycle 6, with a response, at progression or appearance of a new lesion, at end of treatment and in the event of a Skin Flare Reaction  (O) Skin biopsy: At response (PR/CR),	M	(see above)
Peripheral blood immunophenotyping  PI: [name]  Site: Stanford University	Multiparametric flow cytometry and CyTOF  CLIA: N	Exploratory  Purpose: Hypothesis generating  Phenotyping of normal T cell and Sezary cell populations pretreatment and post treatment. Functional phenotyping of T cells will be performed by testing cytokine production after stimulation.	Tissue: Peripheral blood mononuclear cells  Timing:  (M) Prior to IFN-gamma lead-in, Prior to Cycle 1, Prior to Cycle 2, and in the event of a Skin Flare Reaction.	M	(see above)
Serum cytokine and chemokine detection  PI: [name]  Site: Stanford University	Luminex multiplexed ELISA-based cytokine assay  CLIA: N	Exploratory  Purpose: Hypothesis generating  Quantitative measurement of cytokines/chemokines pre and post treatment	Tissue: Serum  Timing:  (M) Prior to IFN-gamma lead-in, Prior to Cycle 1, Prior to Cycle 2, prior to Cycle 6, with response, or progression, at EOT and in the event of a Skin Flare Reaction.	M	(see above)

NCI Protocol #: CITN-13  
 Version Date: March 03, 2020

Biomarker Name a AND Lead PI and Site	Assay (CLIA: Y/N)	Use (Integral, Integrated, or Exploratory) AND Purpose b	Tissue/Body Fluid Tested and Timing of Assay	M/O	Funding Source(s) c
Tumor genotyping and prediction of neoantigens  PI: [name]  Site: Stanford University	Whole exome sequencing  CLIA: N	Exploratory  Purpose: Hypothesis generating and will test the hypothesis that high neoantigen burden is associated with response	Tissue: Skin biopsy and peripheral blood  Timing:  (M) Skin biopsy: Prior to IFN-gamma lead-in, prior to cycle 1, prior to cycle 2, at progression or appearance of a new lesion, at EOT, and in the event of a Skin Flare reaction.  Blood draw: Prior to IFN-gamma lead-in, Prior to Cycle 2, Prior to Cycle 6, with response, at progression, at EOT  (O) Skin biopsy: At response (PR/CR).	M	(see above)
T cell receptor sequencing  PI: [name]/[name]  Site: Fred Hutchinson Cancer Research Center	High throughput sequencing of TCR  CLIA: N	Exploratory  Purposes: Hypothesis generating and to assess responses through  Response assessment through detection of malignant clone and characterization of the T cell repertoire.	Tissue: Skin biopsy and peripheral blood mononuclear cells  Timing:  (M) Skin biopsy: Prior to interferon gamma lead-in, Prior to Cycle 1, prior to Cycle 2, at progression or appearance of a new lesion, EOT, and in the event of a skin flare reaction.  Blood draw: Prior to IFN-gamma lead-in, Prior to Cycle 1, Cycle 2, 6, 10, then every 4 cycles, with progression, response, EOT, and in the event of a Skin Flare Reaction.  (O) Skin Biopsy: At response (PR/CR)	M	(see above)
Kyn/Trp  PI: [name] and TBD  Site: Fred Hutchinson Cancer Research Center and Incyte Corp.	Mass Spec  CLIA: N	Exploratory  Purposes: Hypothesis generating and to assess whether IDO1 activity may be a mechanism leading to treatment failure.	Timing:  (M) Blood draw: Prior to IFN-gamma lead-in, Prior to Cycle 2, 6, 10, then every 4 cycles, with progression, response, EOT, and in the event of a Skin Flare Reaction.	M	(see above)
Microbiome  PIs: [name] and [name]  Site: Fred Hutchinson Cancer Research Center	16S rRNA gene sequencing and WGS  CLIA: N	Exploratory  Purposes: Hypothesis generating and to understand the role of the microbiome in responses to immunotherapy	Timing:  (M) Stool Sample: Prior to IFN-gamma	M	(see above)

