#### 2.5.9 Kyn/Trp Ratio

IDO catabolizes the conversion of Tryptophan to Kynurenine, which has potent immunosuppressant properties. An increase in Kynurenine levels over time, relative to Tryptophan levels, is known to be inhibitory to T cell function. For patients who are failing anti-PD-1 therapy increased Kyn/Trp ratios could indicate that IDO expression may be leading to treatment failure. Kyn/Trp ratios will be assayed in patients receiving a regimen of MK-3475 (pembrolizumab) as measured in peripheral blood at baseline and at specified intervals throughout the trial. We have defined the Kyn/Trp Ratio as a special study because the results may help to elucidate a likely mechanism for anti-PD-1 failure. This mechanism of resistance could potentially be overcome with an IDO inhibitor.

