#### 5.1.1 Mycosis Fungoides/Sézary Syndrome (Treatment Group 1)

##### *Treatment Plan*

- MK-3475 (pembrolizumab) will be administered at a dose of 200 mg every 3 weeks by IV infusion. No dose modification will be allowed.
- IFN-gamma will be initiated at 50 mcg/m^2 administered subcutaneously 3 times a week (e.g., M/W/F or T/Th/Sat).

Regimen Description (Treatment Group 1)					
Agent	Premedication; Precautions	Dose	Route	Schedule	Cycle Length
MK-3475 (pembrolizumab)	None	200 mg	Intravenous Refer to Section 8.1.1 for compatible infusion set materials including in-line filter.	Every 3 weeks (Day 1 of each cycle)	3 weeks
Interferon-gamma-1b	Antihistamines, analgesics, nonsteroidal anti-inflammatory drugs (NSAIDs), anti-depressants. Refer to Section 6.1.5	50 mcg/m  (Dose Varies, see below)	Subcutaneous	Three times weekly (e.g., M/W/F or T/Th/Sat)	Variable

The combination will be administered following the schema above:

- IFN-gamma lead-in treatment x 1 week => opportunity to obtain correlative biomarkers after IFN-gamma monotherapy for correlative studies
- Combination of MK-3475 (pembrolizumab) 200mg every 3 weeks and IFN-gamma 50 mcg/m^2 3 doses per week for 12 weeks
- Followed by MK-3475 (pembrolizumab) continued every 3 weeks up to 2 years. IFN-gamma boost (3 weeks) blocks every 2 cycles (6 weeks) of MK-3475 (pembrolizumab). IFN-gamma will be given 3 weeks on followed by 3 weeks off. If patients are experiencing intolerable toxicities and need additional time off, the investigator may increase time off in 1 week increments up to 3 weeks. A re-assessment of symptoms is made during this time period. The decision to increase time off is at the discretion of the investigator in consultation with the patient. If a patient is tolerating IFN-gamma well, IFN-gamma can be given continuously without break at the discretion of the investigator and in consultation with the patient starting at cycle 7. This option is intended for patients who experienced worsening of disease or associated symptoms during the cycles off of IFN-gamma, or in cases where the investigator believes the patient would otherwise benefit from continuous IFN-gamma therapy.

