- Intra-patient dose increase for IFN-gamma: dose increases by 25 mcg/m^2 can be considered at each boost event if a CR cannot be confirmed at a global clinical assessment, to a max IFN-gamma dose of 100 mcg/m^2. If toxicity seen at higher IFN-gamma dose is deemed intolerable by the treating physician, the IFN-gamma dose can be reduced to the previously tolerable dose.

- The dose of IFN-gamma will be reduced to 25 mcg/m^2 for certain Gr 3 toxicities as outlined in [Section 6.1.4](#), and may be reduced at the investigator discretion to 25mcg/m^2 for constitutional symptoms as in [Section 5.1.1.2](#). If patients are experiencing intolerable toxicities, IFN-gamma may be held for up to a period of 3 weeks at the discretion of the investigator and in consultation with the patient. A re-assessment of symptoms is made during this time period, and treatment may be restarted at any point during the cycle. If such a hold occurs after cycle 5, treatment would recommence at the next planned cycle on IFN-gamma. For example, if IFN-gamma were held throughout cycle 8, the next IFN-gamma treatment would be at the start of cycle 10.

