### 9.1.3 Special Studies

#### 9.1.3.1 *Special Correlative Study #1: Whole Blood Kyn/Trp Ratios*

It is postulated that enhanced IDO expression may occur in patients who fail anti-PD-1 therapy. Thus, Kyn/Trp ratios will be assayed as measured in peripheral blood at baseline and at specified intervals throughout the trial. Evidence of this mechanism of resistance would suggest that some anti-PD-1 failures could potentially be overcome with an IDO inhibitor.

*Collection of Specimens*

Whole blood will be collected into heparinized tubes and processed to frozen plasma at the local lab.

*Handling of Specimen(s)*

Frozen vials of plasma will be batch shipped to the CITN Central Laboratory.

*Shipping of Specimens*

Frozen vials of plasma will be shipped from the CITN Central Laboratory to the Incyte Corporation for testing.

*Site(s) Performing Correlative Study*

The Kyn/Trp analysis will be conducted at Incyte Corporation

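### Group 1 Kyn/Trp samples are taken at differing IFN-gamma states that can become linked to disease status after cycle 6, and the analysis plan takes no account of IFN-gamma exposure.

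*Combined protocol and SAP*

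**What the plan says.** Appendix C (Treatment Group 1, Kyn/Trp row) schedules the draws "Prior to IFN-gamma lead-in, Prior to Cycle 2, 6, 10, then every 4 cycles, with progression, response, EOT" and also at a skin flare reaction. The stated purpose is hypothesis generation and "to assess whether IDO1 activity may be a mechanism leading to treatment failure". Section 2.5.9 gives the reading in advance: "For patients who are failing anti-PD-1 therapy increased Kyn/Trp ratios could indicate that IDO expression may be leading to treatment failure". Section 9.1.3.1 adds the consequence: "Evidence of this mechanism of resistance would suggest that some anti-PD-1 failures could potentially be overcome with an IDO inhibitor".

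On treatment, Section 5.1.1 has a one-week lead-in and 12 weeks of combination, after which "IFN-gamma will be given 3 weeks on followed by 3 weeks off". The Section 10.1 calendar shows IFN-gamma in cycles 1 to 4 and then in even cycles from cycle 6. From cycle 7 a patient who tolerates it may take IFN-gamma without breaks: "This option is intended for patients who experienced worsening of disease or associated symptoms during the cycles off of IFN-gamma", or for patients the investigator otherwise expects to benefit. A dose step of 25 mcg/m², up to 100 mcg/m², "can be considered at each boost event if a CR cannot be confirmed at a global clinical assessment". Footnote a to Section 6.1.4 words the same rule as something that will happen; the two passages should be reconciled.

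Section 13.1.2 plans descriptive summaries of the biomarkers and time-to-event curves by biomarker group. It mentions no IFN-gamma dose, on/off phase or time since last injection.

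**The concern.** The Kyn/Trp study asks one question: does IDO activity accompany failure of treatment? Answering it means comparing ratios in failing patients with ratios in others, or with the same patient's earlier values. One of the two study drugs is an immune-activating cytokine given in blocks, and after cycle 6 its dose and timing can depend on how the disease is doing. If that drug moves the ratio, the comparison mixes a drug effect with a resistance effect, and nothing in the plan separates them. At stake is a mechanistic conclusion that would point towards another drug class. The primary ORR analysis, the stopping rules and the safety review do not use this assay.

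**Working it through.** The documents give no sample size, error rate or effect size for Kyn/Trp, so there is no planned figure to reproduce. The check lays the draws over the dosing calendar and then illustrates the possible size.

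**1. IFN-gamma state at each draw.** Inputs: draw times from Appendix C; on/off cycles from Section 10.1; draws on Day 1 before MK-3475 (Section 10.1, footnote a); three injections a week (Section 5.1.1). An on-cycle holds 3 × 3 = 9 doses.

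| Draw | Preceding cycle (default) | Doses in prior 21 days |
|---|---|---|
| Pre-lead-in | none | 0 |
| Pre-C2 | C1, on | 9 |
| Pre-C6 | C5, off | 0 |
| Pre-C10, C14 ... C34 | odd cycle, off | 0 |
| Response, progression, EOT, flare | either | 0 to 9 |

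**2. Where disease status enters.** A patient on continuous dosing from cycle 7 has 9 doses before the C10 draw: 9 × 50 = 450, 9 × 75 = 675 or 9 × 100 = 900 mcg/m², against 0 for a patient left on the default. Escalation first applies at the cycle 6 boost and continuous dosing at cycle 7, both after the C6D1 sample. Samples up to and including C6D1 are therefore free of disease-driven dosing, although toxicity holds and reductions can still alter exposure.

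**3. How many progressions come later.** Section 2.4.3 gives the monotherapy trial's median PFS as 44 weeks, with 75% progression-free at 6 months. Assuming exponential times, the progression-free share at week 15 (just before C6D1) is 0.5^(15/44) = 0.79 or 0.75^(15/26) = 0.85. Most progressions would then fall where disease-driven dosing is possible.

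**4. Illustration of size.** All of the following are assumptions: 15 failing and 15 responding patients; log ratio normal with SD 0.3 or 0.5; no true difference; being on IFN-gamma multiplies the ratio by 1.25, 1.5 or 2.0; half of the failing patients on IFN-gamma at the draw; two-sided Mann-Whitney test at 5%; 20,000 runs per setting. The spurious difference in mean log ratio is log(multiplier) × (share on among failing − share on among responders). For a multiplier of 2.0 it is 0.693 × (0.5 − 0) = 0.35 with no responders on, 0.693 × (0.5 − 0.25) = 0.17 with a quarter on, and −0.17 with three quarters on.

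| Responders on IFN | False positives, SD 0.3 (×1.25 / 1.5 / 2.0) | SD 0.5 |
|---|---|---|
| 0% | 14 / 33 / 56% | 8 / 16 / 33% |
| 25% | 7 / 11 / 17% | 5 / 7 / 11% |
| 50% | about 5% | about 5% |
| 75% (difference reversed) | 7 / 11 / 17% | 5 / 7 / 11% |

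With equal shares on IFN-gamma the test keeps roughly its nominal rate. In the last row the drug effect works against an IDO signal.

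**5. The missing IFN-only sample.** Appendix C and Section 10.1 draw blood before cycle 1, after the lead-in, for transcriptional, CyTOF, cytokine and TCR assays, but not for Kyn/Trp. The plan therefore has no sample showing what IFN-gamma alone does to this ratio.

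**The case against.** A reader might infer that the design builds in a false IDO signal, with error rates of 14% to 56%. The documents do not support that, for four reasons.

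- No passage says that IFN-gamma changes Kyn/Trp. Section 2.4.5 links it to PD-1 and PD-L1 induction, and Section 2.5.9 links IDO to anti-PD-1 failure. The existence of the effect is an assumption, not only its size.
- The high rates need every responder to be off IFN-gamma. Response draws are event-driven too. Median time to response in the monotherapy trial was 11 weeks (range 8 to 22), and weeks 1 to 12 are all on IFN-gamma here, so early response draws can be on. Progression found at scheduled visits from cycle 6 follows an off cycle on the default calendar. The bias could run either way.
- Escalation is open to PR, SD and PD alike. With 1 CR among 24 patients in the monotherapy trial, it would separate failure from response only weakly. Continuous dosing is the stronger link, but it is discretionary and not confined to patients who worsened.
- The plan's language is tentative, the correlatives are declared not to be endpoints (Section 2.4.5), and no failing-versus-responding test of Kyn/Trp is specified. The error rates above belong to an illustrative test.

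These points limit the concern without removing it. The draws do differ in IFN-gamma state, part of the continuous-dosing rule refers to worsening disease, the reading of a raised ratio is written down, and Section 13.1.2 has no step to account for exposure.

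**Conclusion.** The point holds as a conditional weakness in one exploratory study. If IFN-gamma alters Kyn/Trp, an unadjusted comparison of failing with non-failing patients could create or conceal an apparent IDO-resistance signal. The documents fix neither direction nor size: the illustrated false-positive rate goes from about 5% with equal on-IFN shares to 56% at the extreme, and the shares themselves are assumed. Progressions at or before C6D1 are not touched by disease-driven dosing. It would go too far to say that exposure differs by outcome throughout, or that a positive finding would be a drug artefact. The trial's primary conclusion is unaffected. This is a cheap improvement worth making before the assay results are seen, since an exposure adjustment chosen afterwards would carry less weight.

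**What to change.** Add a short Kyn/Trp paragraph to Section 13.1.2:

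- Report fold change from the pre-IFN sample at C2D1 (scheduled on) and C6D1 (scheduled off) as the comparison free of disease-driven dosing.
- Keep the failure question for later and event-driven samples, but compare samples with the same IFN-gamma status, or adjust for dose and days since last injection.
- Record the Group 1 IFN-gamma dose and last-injection date at each Kyn/Trp draw. An injection log is described only for Group 2 (Section 5.1.2.2), so these data should not be presumed available.
- Optionally, add a Kyn/Trp sample at C1D1 to show the IFN-only effect. Research blood is already drawn then, but Section 9.1.3.1 requires heparinised blood processed locally to frozen plasma, so this means its own 10 mL tube and a calendar change.

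The cost is analysis-plan wording, one small data item, fewer late samples in the matched comparison and, if the option is taken, one extra tube. No dosing change is implied.
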